6.1.3 Other study parameters

Body weight:

Each patient's body weight will be determined at every time point. Relative weight changes will be presented as the percent weight change relative to the weight at baseline.

Height:

Each patient's height will be measured with a SECA ruler at the start of the study. From the measured body weight and height, BMI will be calculated by dividing body weight (kg) by the square of height (m).

Age, gender, type and doses of cytostatics, the number of chemotherapy cycles, education level, smoking and alcohol consumption:

Data on these variables will be determined at baseline by a questionnaire or from the medical files. The doses of the cytostatics will be determined at every time point.

Treatment toxicity:

Treatment toxicity will be monitored by the treating physician according to the Common Toxicity Criteria during the entire study period [48].

MUST:

The Malnutrition Universal Screening Tool (MUST) will be used at baseline to determine the risk of malnutrition.

6.2 Study procedures

A number of things will be set in motion after the patient signs the informed consent. As described earlier, the researcher will register the patient. If the patient is allocated to the intervention group, FoodforCare will be informed by the researcher. FoodforCare will take care of the delivering of the products and will have contact with the AYA's/research assistants about the measurements. Before the start of the intervention, an individual intake will take place with the patient by FoodforCare. During this intake, the composition of the dishes will be tailored to the needs of the patient in terms of composition, diet, taste, flavor and portion size. These dishes will be delivered to the patients by the AYA's/research assistants every three days. Depending on the patient's wishes, the partner or caregiver of the patient can receive the same dishes. In case the patient is allocated to the control group, the AYA's/research assistants are informed to perform the measurements at home at the given time points.

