Intervention and procedure: Inclusion will take place at the department of Medical Oncology at the start of palliative chemotherapy. Patients will be randomly assigned to one of two groups before the start of the second cycle of chemotherapy. The intervention group will receive meals from FoodforCare at Home and the control group will continue their regular diet for 3 weeks between the 2nd and 3rd cycle of chemotherapy. The FoodforCare at Home meals will be delivered at the patient's home by research assistants or AYA's. These are Adolescents and Young Adults with cancer who are also trained to perform the measurements.

Main study parameters/endpoints: The main study parameter is quality of life of patients receiving FoodforCare at Home compared with patients receiving their usual diet. This will be evaluated by the EORTC-QLQ-c30 at all time points. The secondary endpoints are patient satisfaction, nutritional status, nutritional intake, performance scale, medication use, symptoms and quality of life of the partner/caregiver.

Nature and extent of the burden and risks associated with participation, benefit and group relatedness: There are no additional tests or hospital tests necessary for the patient. This study will not confer any no additional risks. Food will be delivered within the expiration dates and the meals will be prepared according to the regular hygienic and food safety criteria that are valid. Possible serious reactions to the meals will be noted as SAE's.

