3. STUDY DESIGN

A randomized controlled trial will be performed in palliative abdominal oncology patients at home. Inclusion will take place at the department of Medical Oncology at the start of palliative chemotherapy. The study is intended to be performed from March 2017 to July 2018. Patients will be randomly assigned to one of two groups before the start of the second cycle of chemotherapy because it is expected that FoodforCare at Home will make the largest difference during this cycle. The intervention group will receive meals from FoodforCare at Home and the control group will continue their regular diet for three weeks from the second cycle of chemotherapy until the next cycle of chemotherapy. Before the start of this study, a pilot study will be performed to determine whether the intervention is feasible in terms of logistics and delivery of the meals for example.

Measurements will take place at four time points during the study period i.e. before the start of chemotherapy, at the 2nd cycle of chemotherapy, at the 3rd cycle of chemotherapy and three month after T3 (figure 1). These measurements will be performed by AYA's/research assistants who will visit the patients at home. Time point 1, before the start of chemotherapy, will serve as the baseline measurement. At this moment, informed consent will be obtained and signed by the patient and the MUST score will be determined. Quality of life of patient and caregiver, nutritional intake, nutritional status, functional status and medication use will be assessed at all time points. For quality of life, the EORTC-QoL-C30 questionnaire will be filled in by the patients and the Caregiver Reaction Assessment by their caregivers. Nutritional status will be assessed using the handgrip strength measurement, the PG-SGA and performance scale by means of the Karnofsky score and the SPPB. Data on nutritional intake will be recorded using a 3-day food diary, which the patients will fill in by themselves. Medication use will be obtained from the patient's medical file. Additionally, during the intervention period, patients will record their symptoms using 'Utrecht Symptoom Dagboek' and medication use will be assessed by using a diary. At time point 3, patient satisfaction in the intervention group will be assessed by the Net Promoter Score with additional questions. An overview of the measurements can be found in table 1.

Figure 1. Flowchart of the study design of the FoodforCare at Home study.

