6.3 Randomisation, blinding and treatment allocation

Patients will be randomized into two groups at the department of medical oncology in the Radboudumc. This will be performed by using the randomization program which is part of the clinical data management system 'Research Manager'. This validated web based data management system will be used during the entire study. The researcher will have a password to the randomization program. After randomization, a study number will be assigned to the patient. The researcher documents the patient information and study number in a designated source document. The study number and birth date will be listed on all study documents. The randomization will be stratified on tumor type and type of chemotherapy because of the possible effect on the primary outcome. This stratification reduces the risk of an uneven distribution of prognostic factors. We will not stratify for other characteristics; the exclusion criteria will contribute sufficiently to a homogenous patient population.

Blinding is not possible for the coordinating researcher, since one group will receive FoodforCare at Home and the other group will receive no additional products. Patients have to be aware of in which group they are in. Whether blinding is possible for the AYA's/

research assistants will be examined during the pilot study. In that case, patients will be asked not to tell the AYA's/research assistants in which group they are allocated.

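### Under 6.2 one pool of assistants both delivers the meals and measures outcomes, with contact that differs by arm, so the only blinding safeguard in 6.3 cannot work as written

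*Combined protocol and SAP*

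**What the plan says.** **Delivery.** The Summary states: "The FoodforCare at Home meals will be delivered at the patient's home by research assistants or AYA's". Section 6.2 gives the frequency: "These dishes will be delivered to the patients by the AYA's/research assistants every three days". Section 5.1 gives it as twice a week. Only the intervention arm receives meals.

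**Measurement.** Section 3 assigns the four measurement rounds to the same category of staff: "These measurements will be performed by AYA's/research assistants who will visit the patients at home". The Summary confirms the overlap, describing the young adults with cancer who help with delivery as people "who are also trained to perform the measurements".

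**Notification.** Section 6.2 describes two routes. For one arm: "If the patient is allocated to the intervention group, FoodforCare will be informed by the researcher", after which the supplier "will have contact with the AYA's/research assistants about the measurements". For the other: "In case the patient is allocated to the control group, the AYA's/research assistants are informed to perform the measurements at home", with no mention of the supplier.

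**Blinding.** Section 6.3 rules out blinding for the coordinating researcher and the patients. For the assistants it leaves the question to the pilot. If blinding proves possible, "patients will be asked not to tell the AYA's/research assistants in which group they are allocated". No other safeguard is described.

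**The concern.** Section 6.3 treats the patient as the only channel through which an assistant could learn the arm. Section 6.2 opens two more: carrying the meals, and being contacted about measurements by a different route in each arm. A patient's silence closes neither.

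What is at stake is the comparison of outcomes that the assistants help to determine. Section 6.1.2 has them complete the PG-SGA in consultation with the patient, and the Karnofsky score is also settled in consultation. Handgrip and SPPB are performance tests carried out at the same home visits. These outcomes carry secondary objectives 3 (nutritional status) and 4 (functional status). If the assessor knows the arm, part of any difference on them could reflect the rating rather than the meals.

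**Working it through.** The plan gives no figure on this point, so the main check is to set the sections side by side.

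1. *Who knows the arm through delivery?* Only intervention patients get meals (5.1, 6.2), so anyone who delivers to a patient knows that patient's arm.
2. *Can that person also be the assessor?* Delivery (Summary, 6.2) and measurement (Summary, section 3) are assigned to the same pool. No section says that a patient's assessor must be someone who has not delivered to that patient.
3. *Would separating the people be enough?* Not under 6.2 as written. Supplier contact about measurements appears only under intervention allocation, and the control notice is a separate step. An assistant who never delivered could still infer the arm from who made contact.
4. *Does the safeguard in 6.3 address either channel?* No. It concerns only what the patient says.
5. *Which measurements are exposed?* T1 precedes randomisation and is unaffected. T2 is taken at the second cycle, when few or no meals can have been delivered, although the notice could already reveal the arm. T3 and the visit three months later follow the whole delivery period.

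**Number of delivery contacts.** Every three days over three weeks: 21 / 3 = 7. Twice a week over three weeks: 2 × 3 = 6. That is about 6 to 7 in the intervention arm and none in the control arm.

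**Illustration of size for one staff-assessed outcome.** Inputs are 164 randomised and 20% drop-out (section 4.4). The rating shift is an assumption, since the documents give no value for it.

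- Evaluable: 164 × 0.8 = 131.2, or 65.6 per arm.
- Standard error of the difference, in SD units: √(2 / 65.6) = 0.175.
- Two-sided rejection probability at the 5% level with no true effect and a shift of δ SD: Φ(−1.96 + δ/0.175) + Φ(−1.96 − δ/0.175).

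| Assumed shift (SD) | Shift / SE | Chance of a false positive |
|---|---|---|
| 0 | 0 | 5% |
| 0.1 | 0.57 | about 9% |
| 0.2 | 1.15 | about 21% |
| 0.3 | 1.72 | about 40% |

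This is a simple comparison at one time point. It does not reproduce the mixed model of sections 8.2 and 8.3.

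**The case against.** The strongest reply is that 6.3 makes no claim of blinding. It defers the question to a pilot, which section 3 says will examine logistics and delivery, and who delivers and who measures is a logistics question. This stands in part: the matter is openly deferred, and a reader who infers that assessor blinding is impossible in this trial goes too far. The documents name a category of staff. They do not say that one individual both delivers to and measures a given patient, and a rota could keep the roles apart. What remains is that 6.2 contains no such rota, so a pilot of the procedure as written would test one that unblinds itself.

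Three other stronger readings are also unsupported.

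- *That assistants are told the allocation.* Section 6.2 does not say so. That they can learn it follows from the delivery task and the arm-dependent notices.
- *That the supplier takes part in measuring one arm.* The text describes contact about measurements, which may be no more than visit coordination. No section gives the supplier a role in rating or recording outcomes, and section 10.1 has the researchers enter the data.
- *That the primary result is compromised by this defect.* Patients complete the QLQ-C30 themselves and must know their group, so it stays open to bias whether or not assistants are blinded. The documents do not say whether an assistant is present when it is completed.

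It is also fair to say that handgrip is partly standardised in 6.1.2 (repeated measurements, fixed posture), and that the food diary, symptom diary and medication data are not rated by the assistants. The exposure is clearest for PG-SGA and Karnofsky.

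**Conclusion.** The conflict between 6.2 and 6.3 is real, within limits. Under 6.2 as written there is no separation of deliverer and assessor for a given patient and no arm-neutral way of arranging measurements, so asking patients to stay silent cannot achieve the blinding that 6.3 contemplates.

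The direct consequence is a risk of assessment bias in PG-SGA, Karnofsky, SPPB and handgrip after randomisation, mainly at T3 and later. Its size cannot be derived from the documents. The range of about 9% to 40% rests entirely on assumed shifts of 0.1 to 0.3 SD, with about 131 evaluable patients and one outcome considered alone. It must not be read as the type I error of the primary test. The point merits an amendment because the remedy is cheap and serves an aim that 6.3 already states.

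**What to change.** Amend 6.2 and 6.3 as follows.

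- Within the existing pool, the assistant who measures a patient after randomisation has not delivered meals to that patient and is not told the allocation.
- The researcher, not the supplier, schedules measurements in both arms, using an identical message.
- The pilot tests this procedure, including whether assessors in practice remain unaware of the arm.
- Any outcome still rated by an unblinded assistant is reported as such.

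The request to patients in 6.3 stays and becomes useful once the other two channels are closed.

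The cost is rota planning and some extra travel, because a measurement visit can no longer be combined with that person's delivery. Patients may live up to 40 km away and the size of the pool is not stated, so the pilot should confirm that the rota is workable. The sample size and the analysis do not change.

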6.3 Randomisation, blinding and treatment allocation

Patients will be randomized into two groups at the department of medical oncology in the Radboudumc. This will be performed by using the randomization program which is part of the clinical data management system 'Research Manager'. This validated web based data management system will be used during the entire study. The researcher will have a password to the randomization program. After randomization, a study number will be assigned to the patient. The researcher documents the patient information and study number in a designated source document. The study number and birth date will be listed on all study documents. The randomization will be stratified on tumor type and type of chemotherapy because of the possible effect on the primary outcome. This stratification reduces the risk of an uneven distribution of prognostic factors. We will not stratify for other characteristics; the exclusion criteria will contribute sufficiently to a homogenous patient population.

Blinding is not possible for the coordinating researcher, since one group will receive FoodforCare at Home and the other group will receive no additional products. Patients have to be aware of in which group they are in. Whether blinding is possible for the AYA's/

research assistants will be examined during the pilot study. In that case, patients will be asked not to tell the AYA's/research assistants in which group they are allocated.

6.4 Withdrawal of individual subjects

6.4.1 Specific criteria for withdrawal

Subjects can end their participation in the study at any time for any reason if they wish to do so without any consequences. The investigator can decide to withdraw a subject from the study for urgent medical reasons.

6.5 Replacement of individual subjects after withdrawal

During the inclusion period, additional patients will be included to be able to achieve the necessary number of patients in case of withdrawal of patients during the study.

6.6 Follow-up of subjects withdrawn from treatment

When patients withdraw from the study after time point 3, these data may (if authorized by the patient) be used for analyses.

6.7 Premature termination of the study

Situations in which the study should be terminated prematurely are not expected. Moreover, the use of 'usual care' and the FoodforCare products bring no additional risk to the patients. Therefore, we do not expect a large number of adverse events in either group.

7. SAFETY REPORTING

7.1 Section 10 WMO event

In accordance to section 10, subsection 1, of the WMO, the investigator will inform the subjects and the reviewing accredited METC if anything occurs, on the basis of which it appears that the disadvantages of participation may be significantly greater than was foreseen in the research proposal. The study will be suspended pending further review by the accredited METC, except insofar as suspension would jeopardise the subjects' health. The investigator will take care that all subjects are kept informed.

7.2 AEs, SAEs and SUSARs

7.2.1 Adverse events (AEs)

Adverse events are defined as any undesirable experience occurring to a subject during the study, whether or not considered related to the Food for Care products. All adverse events reported spontaneously by the subject or observed by the investigator or his staff will be recorded.

Possible adverse events include: nausea, vomiting, gastrointestinal complaints. These events will already be identified by the EORTC-QoL-C30 questionnaire and the 'Utrecht Symptoom Dagboek'. Other side effects including severe (very rare) side effects are not expected to occur. However, it is important to monitor these side effects as well and therefore, the patient will be asked to contact a staff member and the researchers directly when side effects are present. Our proposition will be to only register adverse events that have a possible causal relationship with the given food products. Examples of these events include gastrointestinal complaints and allergic reactions.

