5. INVESTIGATIONAL PRODUCT

5.1 Name and description of investigational product(s)

In a period of 1.5 year, 164 patients will be randomized into two groups. The intervention group will receive meals from FoodforCare at Home and the control group will continue their usual diet for 3 weeks. The FoodforCare at Home concept consists of five to six small protein and energy enriched meals that will be delivered twice a week. After an individual intake, the composition of the dishes will be tailored to the needs of the patient in terms of composition, diet, taste, flavor and portion size. Besides the meals, patients in the intervention group will also receive an information leaflet about the importance of protein during treatment and how to reach their protein requirements. The control group has no restrictions to their diet. The dishes are prepared every day by Maison van den Boer.

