7.2.2 Serious adverse events (SAEs)

A serious adverse event is any untoward medical occurrence or effect that at any dose:

- results in death;
- is life threatening (at the time of the event);
- requires hospitalisation or prolongation of existing inpatients' hospitalisation;
- results in persistent or significant disability or incapacity;
- is a congenital anomaly or birth defect;
- Any other important medical event that may not result in death, be life threatening, or require hospitalization, may be considered a serious adverse experience when, based upon appropriate medical judgement, the event may jeopardize the subject or may require an intervention to prevent one of the outcomes listed above.

Our proposition will be to only register serious adverse events that have a possible causal relationship with the given food products. Examples of these events include gastrointestinal complaints and allergic reactions, which cause the above mentioned.

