7.3 Follow-up of adverse events

All AEs will be followed until they have abated, or until a stable situation has been reached. Depending on the event, follow-up may require additional tests or medical procedures as indicated, and/or referral to the general physician or a medical specialist. (S)AEs will be reported till the end of study.

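### Two adverse-event capture rules stand unreconciled; if the food-related filter governs, no control-arm AE or SAE can be registered, and deaths, admissions and allergic events have no between-arm count

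*Combined protocol and SAP*

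**What the plan says.** Section 7.2.1 opens with a definition that covers any undesirable experience during the study, "whether or not considered related to the Food for Care products". It continues: "All adverse events reported spontaneously by the subject or observed by the investigator or his staff will be recorded". Later in the same section comes the opposite rule: "Our proposition will be to only register adverse events that have a possible causal relationship with the given food products".

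Section 7.2.2 lists the usual seriousness criteria, including death and hospitalisation, and then applies the same filter: "Our proposition will be to only register serious adverse events that have a possible causal relationship with the given food products".

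Other sections bear on which rule is meant:

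- Section 7.3: "All AEs will be followed until they have abated, or until a stable situation has been reached". No causality restriction is attached.
- Section 6.7: "Therefore, we do not expect a large number of adverse events in either group". This presupposes that events can be counted in both groups.
- The Summary and section 5.3 say only that possible serious reactions to the meals or products are noted as SAEs, which fits the filter.

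On exposure, section 5.1 says "the control group will continue their usual diet for 3 weeks", and section 6.3 says "the other group will receive no additional products".

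**The concern.** Staff are given two incompatible instructions about which events enter the trial's safety data. Under the first, events from both arms are collected. Under the second, an event must be possibly caused by the food that the study gives, and a control patient is given none. The second rule would leave a one-sided safety record: some events from the intervention arm, selected by a judgement of cause, and nothing to set beside them.

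This matters most for serious events. The patients are receiving palliative chemotherapy and are followed to three months after T3, so deaths and admissions are to be expected in both arms. Survival and hospitalisation are not listed among the study parameters in section 6.1, which makes SAE registration the natural place to capture them. Without a count by arm, the trial's own data could not be used to check by arm the premise, stated in the Summary and in sections 5.3, 6.7 and 11.2, that the meals carry no additional risk.

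**Working it through.** The plan gives no figure to reproduce. The check is a reading of the sections against each other, plus a small illustration.

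**Step 1. Which rule governs?**

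| Section | What it implies | Fits |
|---|---|---|
| 7.2.1, definition and recording sentence | all AEs, regardless of cause | record all |
| 7.3 | all AEs followed up | record all |
| 6.7 | AEs considered in both groups | record all |
| 7.2.1, later sentence | only possibly food-related AEs | filter |
| 7.2.2, last paragraph | only possibly food-related SAEs | filter |
| Summary and 5.3 | serious reactions to the meals noted as SAEs | filter |

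No section ranks one rule above the other. None defines *record* (for example, source notes) and *register* (for example, database or committee reporting) as separate steps.

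**Step 2. What does the filter do in each arm?**

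- *Control arm.* Registration requires a possible causal link with the given food products. By sections 5.1 and 6.3 the exposure to those products is nil. The registrable count is therefore 0 AEs and 0 SAEs, whatever the true rate. Section 11.2 notes that the dishes are widely served in the hospital, so an admitted control patient might eat them, but that is not food given by the study.
- *Intervention arm.* Entry depends on judging whether an event in a patient on chemotherapy may come from the food. No assessor is named. Section 6.3 says the coordinating researcher and the patients cannot be blinded, and leaves blinding of the assistants to the pilot.

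**Step 3. What is still captured in both arms?**

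- EORTC symptom scales: questionnaire at all four time points; symptom scales a secondary endpoint (section 6.1.1).
- Symptom diary: daily for the 3-week intervention period, with severity compared between groups (sections 6.1.2 and 8.3).
- Toxicity: monitored by the treating physician throughout (section 6.1.3), with no arm restriction. Section 8 plans no between-arm analysis of it.
- Deaths, hospitalisations and allergic reactions: no section says that any of these instruments collects them systematically. The Karnofsky scale has a level for death, but it is scored in consultation with the patient. Section 8 plans no between-arm analysis of AEs or SAEs.

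The named gastrointestinal symptoms therefore have a comparator. SAEs and allergic events do not if the filter governs.

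**Step 4. Illustration of scale.** Planned patients per arm: 164/2 = 82 (section 5.1). The documents give no SAE rate, so I assume that 5% to 20% of patients have an SAE, with 10% as a middle value:

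- 82 × 0.05 = 4.1
- 82 × 0.10 = 8.2
- 82 × 0.20 = 16.4

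Under the filter, about 4 to 16 control patients with an SAE would appear as 0.

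**Step 5. What would full registration be able to show?** Power to detect a doubling, two-sided 5%, normal approximation: Φ(d/SE − 1.96), with SE = √[(p₁(1−p₁) + p₂(1−p₂))/82].

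- 5% v 10%: SE = √[(0.0475 + 0.09)/82] = 0.0409; Φ(0.05/0.0409 − 1.96) = Φ(−0.74), about 23%.
- 10% v 20%: SE = √[(0.09 + 0.16)/82] = 0.0552; Φ(0.10/0.0552 − 1.96) = Φ(−0.15), about 44%.
- 20% v 40%: SE = √[(0.16 + 0.24)/82] = 0.0698; Φ(0.20/0.0698 − 1.96) = Φ(0.90), about 82%.

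The case for symmetric registration is therefore an unbiased descriptive comparison, not a powered test.

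**The case against.** The best defence is that the two verbs mean different things. All events go into source notes, and the filter, worded as a proposition, asks the committee to accept reduced formal registration, much as section 9.4 asks for release from subject insurance. For ordinary food already served in the hospital, with monitoring classed as negligible (section 10.2), that would be proportionate. The Summary and section 5.3 suggest that the limit on SAEs is deliberate. There is also no safety objective in section 2, and the absence of added risk is a premise of the trial rather than a claim to be tested.

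Part of this stands. A low-risk intervention can justify light safety reporting, and the wording may well have been meant that way. But the documents never draw the distinction between the verbs, no settled rule follows the proposition, and sections 7.2.1 and 7.3 point the other way. If that was the intent, a clarifying sentence is still needed.

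Several stronger readings are tempting and should be resisted:

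- *The control arm will have no safety data.* The zero holds only if the filter governs, which is unresolved.
- *There is no comparator for nausea, vomiting and gastrointestinal complaints.* There is, through the EORTC scales and the diary (Step 3).
- *Most intervention-arm SAEs would be missed.* The documents give no basis for this. The threshold is only a possible relationship, and gastrointestinal complaints are the protocol's own example of an event to register.
- *Full registration would reveal a doubling of risk.* At an assumed 10% it would do so less than half the time (Step 5).
- *The trial would not know of deaths.* Drop-out is monitored and medical files are a data source. What is lacking is a stated count by arm.

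**Conclusion.** The concern holds as a contradiction between capture rules with a conditional consequence. The contradiction itself needs no assumption, since both rules stand in section 7.2.1. The consequence depends on the filter governing: registrable control-arm AEs and SAEs are then 0 by logic, and the intervention-arm count depends on an open-label causality judgement by an unnamed assessor.

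The practical gap is confined mainly to SAEs and allergic events. Its size cannot be fixed from the documents; the figure of about 4 to 16 unregistered control patients rests wholly on the assumed 5% to 20% rate. The primary quality-of-life endpoint is not invalidated. This should be corrected because it bears on freedom from bias in the safety record and is cheap to repair.

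**What to change.** Reconcile sections 6.7, 7.2.1, 7.2.2 and 7.3, and align the remarks on serious reactions in the Summary and section 5.3, so that one capture rule applies identically to both arms over the same stated period.

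1. At least for SAEs (including deaths and hospitalisations) and allergic events, register every event regardless of cause, with relatedness to the food as a separate field. Name who assesses it.
2. If a lighter rule is kept for non-serious gastrointestinal events, say that the EORTC symptom scales and the diary serve as their between-arm record.
3. If *record* and *register* are meant as different steps, define both and say which data set each feeds.
4. Add to section 8 a descriptive table of SAE and allergic-event counts by arm, without a formal test.

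The cost is protocol wording and modest extra data entry, much of it from medical files that the study already uses. The downside is some registration of chemotherapy- and disease-related events that have nothing to do with the meals; the relatedness field deals with that.
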